9.2.3 Study visits

Patients will be enrolled consecutively and will be followed over an observational period of approximately 12 weeks. Two study visits will be performed.

Patients will be attributed to either group (triple therapy or Spiolto® Respimat®) on the investigator's discretion and patient's consent before study start at visit 1 (Baseline).

If possible and manageable and in compliance with the investigator's decision, a 1:1 group distribution of the patients included per site should be aimed at. However, a strict distribution scheme is not given.

At Visit 1 (baseline), after information and signature of the Informed Consent Form, the patient will be included into the NIS. The patient will of course have enough time for considering study participation.

At Visit 2, after approximately 12 weeks of treatment, the observation of the patient will end. The respective exams and data to be collected are listed in [Table 9.2.3.1](#).

Table 9.2.3.1: Visit flow chart and data collection parameters

| Parameter | Visit 1; baseline visit | Visit 2; approx. 12 weeks after baseline visit |
|--|-------------------------------|---|
| Informed Consent | X | |
| Specialization of attending physician (GP, pulmonologist, internal specialist) | X | |
| Inclusion / Exclusion Criteria | X | |
| Patient demographics (age, gender, height, and weight) | X | |
| History of COPD | X | |
| Rationale for changing COPD maintenance therapy | X | |
| Number and severity of exacerbations in the last 12 months | X | |
| Number of exacerbations leading to hospitalization in the last 12 months | X | |
| Device training (yes/no), reason for no training | X | |

Table 9.2.3.1 (cont'd): Visit flow chart and data collection parameters

| Parameter | Visit 1; baseline visit | Visit 2; approx. 12 weeks after baseline visit |
|--|-------------------------------|---|
| COPD severity based on GOLD assessment ^{iv} (GOLD patient groups) | X | |
| GOLD spirometric classification, if available ^v , incl. date of examination | X | |
| Eosinophils in peripheral blood, if available | X | |
| Smoking history, current status, pack-years | X | |
| Concomitant diseases / Comorbidities | X | X |
| Current COPD related and other relevant concomitant medication | X | X |
| mMRC breathlessness scale, completed by the patient | X | X |
| Health and functional status by CAT TM questionnaire, completed by patient | X | X |
| General condition of patient evaluated by Physician's Global Evaluation (PGE) | X | X |
| Safety: Adverse Drug Reactions (serious and non-serious), fatal AEs, pregnancy | X | X |
| Patient satisfaction with inhaler, inhalation and treatment and handling | X | X |
| Patient's willingness to continue or discontinue treatment with either triple therapy or Spiolto [®] Respimat [®] after the study (yes/no) | | X |
| Rationale for treatment discontinuation (if applicable) | | X |

9.2.4 Study discontinuation

Boehringer Ingelheim reserves the right to discontinue the study overall or at a particular study site at any time for the following reasons:

1. Failure to meet expected enrolment goals overall or at a particular study site
2. Emergence of any efficacy/safety information that could significantly affect continuation of the study, or any other administrative reasons
3. Violation of the observational plan or the contract by a study site or investigator, disturbing the appropriate conduct of the study

9.3 VARIABLES

The following parameters will be collected and assessed at visit 1 and/ or visit 2:

^{iv} GOLD patient group (A, B, C or D) will be automatically calculated within the eCRF based on available exacerbation history, mMRC and CAT

^v GOLD stage 1-4 spirometric classification of airflow limitation based on post-bronchodilator FEV₁

- Specialization of attending physician (GP, pulmonologist, internal specialist)
- Patient demographics (age, gender, height, weight)
- History of COPD
- Rationale for changing COPD maintenance therapy
- Reported number and severity of exacerbations in the last 12 months
- Number of exacerbations leading to hospitalization in the last 12 months according to medical files
- Device training yes/no, reason for no training
- GOLD patient groups (A, B, C, D, calculated1) based on GOLD guidelines 2019
- GOLD spirometric classifications (1, 2, 3, 4 and date of exam, if available 2)
- Eosinophils in peripheral blood and date of exam, if available
- Smoking history, current status (current smokers, former smokers, and never smokers) and pack-years
- Concomitant diseases / comorbidities such as cardiovascular disease, diabetes mellitus, musculoskeletal impairment, renal diseases, liver diseases, osteoporosis, gastroesophageal reflux (GERD)
- Current (within the last 6 months) COPD related and other relevant concomitant medication such as beta-blockers, beta-agonists, corticosteroids, or proton pump inhibitors at date of Visit 1
- Assessment of the severity of dyspnea based on the Modified Medical Research Council Questionnaire (mMRC), completed by the patient
- Health and functional status by CATTM questionnaire, completed by the patient
- General condition of patient based on Physician's Global Evaluation (PGE) at the beginning and at the end of the study
- Safety: ADRs (serious and non-serious), fatal AEs, pregnancies during the study
- Patient satisfaction with inhaler, inhalation, treatment and handling
- Patient's willingness to continue or discontinue treatment with either triple therapy or Spiolto[®] Respimat[®] after the study (yes/no)
- Rationale for treatment discontinuation (if applicable)

9.3.1 Exposures

Patients will be treated with Spiolto[®] Respimat[®] or triple therapy and be observed for approximately 12 weeks.

Spiolto[®] Respimat[®] contains

- the long-acting anticholinergic tiotropium bromide. The dose dispensed is 2.5 micrograms of tiotropium per puff, equivalent to 3.124 micrograms tiotropium bromide 1 H₂O. The dose dispensed is the quantity available to patients after crossing the mouthpiece.
- the selective beta₂-adrenoceptor agonist olodaterol. The dose dispensed is 2.5 micrograms of olodaterol per puff (as olodaterol hydrochloride). The dose dispensed is the quantity available to patients after crossing the mouthpiece.

The recommended daily dose of Spiolto® Respimat® for adults is 5 micrograms of tiotropium ion (tiotropium) plus 5 micrograms of olodaterol, equivalent to inhaling 2 puffs from the Respimat® inhaler once daily at the same time of day.

The Summaries of Product Characteristics on Spiolto® Respimat® is contained in the NIS ISF in the “Summary of Product Characteristics” section.

Note: The recommended doses stated in the Summary of Product Characteristics should not be exceeded.

Other LAMA, LABA and/or ICS therapy will be performed according to label as described in the respective SmPCs.

9.3.2 Outcomes

9.3.2.1 Primary outcomes

1. Difference between mMRC score at baseline (visit 1) and mMRC score after end of observation (ca. 12 weeks of treatment, Visit 2)
2. Difference between CAT™ score at baseline (visit 1) and CAT™ score after end of observation (ca. 12 weeks of treatment, Visit 2)

The primary outcomes are reported in a descriptive manner, will be compared in an explorative manner and are not safety outcomes.

9.3.2.2 Secondary outcomes

Secondary endpoints to be determined and compared in an exploratory manner include

- patients' general condition according to the Physician's Global Evaluation (PGE) score at baseline and end of the observation period,
- patient satisfaction with inhaler and therapy at end of observation period according to a seven-point ordinal scale (ranging from very dissatisfied to very satisfied as documented in non-interventional BI studies (BI 1237-0042, 1237-0043, 1237-0044, 1237-0045, 1237-0065, 1237-0072),
- proportion of responders with $\Delta_{\text{mMRC}} \geq 1$ and the proportion of responders with $\Delta_{\text{CAT}} \geq 2$.

The secondary outcomes are not safety outcomes.

9.4 DATA SOURCES

Medical records collected through routine clinical care will be used to assess the inclusion/exclusion criteria of patients. Such medical records will be used for patient demographics, smoking history, collection of previous COPD medication, concomitant diseases, and concomitant medication.

All patients will be enrolled consecutively.

9.4.1 PGE

The treating physician will use the Physician's Global Evaluation (PGE) to evaluate the general condition of the patient on an 8-point ordinal scale from 1 (very poor) to 8 (excellent). PGE will be completed before and approx. 12 weeks after treatment initiation.

9.4.2 Symptomatic Burden: mMRC and CATTM

The modified Medical Research Council (mMRC) scale is a 5-point (0–4) scale based on the severity of dyspnoea. The mMRC will be used to assess the breathlessness state of the patient with just one question: "When do you experience dyspnoea?", covering five everyday activities, potentially leading to dyspnoea and giving an according rate of 0 to 4 points. The MCID is a change of 1.0 point. It will be applied before the treatment and after approximately 12 weeks of treatment

The COPD Assessment Test (CATTM) was developed as a simple instrument to assess health status in patients with COPD¹². The CATTM consists of eight items, each formatted as a semantic six-point differential scale, making the tool easy to administer and easy for patients to complete³⁵. These eight items cover cough, phlegm, chest tightness, breathlessness when going up hills/stairs, activity limitations at home, confidence leaving home, sleep and energy. Each item is scored from 0 to 5 giving a total score range from 0 to 40, corresponding to the best and worst health status in patients with COPD, respectively³⁴. The MCID is a change of 2.0 points³⁶.

The questionnaire will be filled out by the patient and entered into the database. Patients will be asked to complete the CATTM in order to evaluate their health and functional status before treatment with Spiolto[®] Respimat[®] or triple therapy, respectively, and after approximately 12 weeks.

Additionally, the mMRC stage and CATTM scores collected from the patient as well as the exacerbation history will be used to automatically calculate the GOLD patient group (A, B, C, or D) in the eCRF.

9.4.3 Patient Satisfaction

The 7-item satisfaction scale with divisions from very dissatisfied to very satisfied to be completed at Visit 1 and Visit 2 to measure patient satisfaction with inhaler use, is a Likert-scale without validation status for the intended use. However, the application of Likert-Scales has been well established in a range of comparable situations^{37, 38, 39}.

Patient's willingness to continue treatment is assessed by a yes/no question plus reasons for non-willingness.

9.5

STUDY SIZE

9.5.1 Sample size justification

It should be noted that the study is generally to be considered exploratory in design. It is further recognized that the multivariable, observational setting complicates a realistic and reliable sample size calculation, e.g. due to the influence of potential confounding variables and dropout (both during study conduct and matched analyses). The sample size calculation/justification given below can therefore only provide a rough estimate of statistical power in an exploratory real-world setting. The sample size is based on the assumption that Spiolto® Respimat® is at least non-inferior compared to any triple therapy using two-sample t-tests (one-sided alpha-level 2.5% and 90% power). The respective MCIDs are treated as non-inferiority margins (to the authors knowledge, established non-inferiority margins are lacking with respect to both endpoints).

The MCID regarding mMRC is 1 point. Based on the real world evidence study by Buhl et al. and BI data, a standard deviation (SD) of 1 point is assumed for the mMRC⁴⁰. The MCID regarding CAT™ is 2 points. Based on the real world evidence study by Buhl et al., a SD of 7 points is assumed for the CAT™⁴⁰.

44 patients overall (22 per group) are required to assess non-inferiority between Spiolto® Respimat® and triple treatment regarding the mMRC. We expect that data of about 40% of patients will not be available for evaluation at the end of the study: a drop out of 10% is based on experiences with German NIS such as BI 1237-0042. An additional drop out of 30% appears likely due to the need to discard patients which cannot be matched (this is based on similar experiences by Buhl et al.⁴¹). Thus, when taking into account this dropout, a total number of 74 patients (37 patients per group) is required to evaluate non-inferiority with respect to the mMRC score.

518 patients overall (259 per group) are required to assess non-inferiority between Spiolto® Respimat® and triple treatment regarding the CAT™. For reasons as outlined above, we expect that data of about 40% of patients will not be available for evaluation at the end of the study. Thus, when taking into account this dropout, a total number of 864 patients (432 patients per group) is required to evaluate non-inferiority with respect to the CAT™ score.

Because mMRC and CAT™ are both of interest as primary endpoints here, the required sample size for the NIS equals the higher of the two respective estimates, i.e. 864 patients in total (432 patients per group).

Patients will be attributed to either group (triple therapy or Spiolto® Respimat®) on the investigator's discretion and patient's consent at visit 1. If possible and manageable and in compliance with the investigator's decision, a 1:1 group distribution of the patients included per site should be aimed at. However, a strict distribution scheme is not given.

Measures to be considered in case of substantially unequal recruitment include the early closing one of the treatment arms earlier (i.e., when its target size is reached) and the analysis of unequal group sizes (1:2, 1:3 or 1:4).

9.6 DATA MANAGEMENT

A data management plan (DMP) will be created to describe all functions, processes, and specifications for data collection, cleaning and validation. The electronic Case Report Forms (eCRFs) will include programmable edits to obtain immediate feedback if data are missing (also negative answers, unknown), out of range, illogical or potentially erroneous.

These rules may encompass simple checks such as range validation or presence/absence of data. Concurrent manual data review may be performed based on parameters dictated by the DMP. Ad hoc queries to the sites may be generated and followed up for resolution.

A source data quality audit may be initiated to ensure that the data in the database is accurate. Source data verification (SDV) will be performed at each recruiting site and further at sites identified by a risk-based approach as needed.

The database will be housed in a physically and logically secure computer system maintained in accordance with a written security policy. The system will meet the standards of the International Committee on Harmonization guideline E6R1 regarding electronic study data handling and the safety requirements of the FDA (US Food & Drug Administration) concerning systems for the data acquisition of clinical studies in accordance with "Title 21 Code of Federal Regulations (21 CFR Part 11): Electronic Records; Electronic Signatures. Patient confidentiality will be strictly maintained.

9.6.1 Data Entry / EDC

Data entry into the eCRF follows the instructions in the EDC system user manual and is further supported by help and hint texts. Support documents will also be provided within the online system documents, which give explanations to basic functions and field types in the eCRF.

With data entry into the EDC system, all changes and user information will be saved in an audit trail.

The data review and validation steps for a project are defined in the data validation plan (DVP).

The DVP includes all definitions of electronic checks and the defined manual checks, which will be performed directly in the EDC system or can be based on listings.

Electronic edit checks (eChecks) are performed automatically and directly when entering data into the eCRF. Missing or implausible data entries or are indicated to the user immediately.

Manual Checks are applied to verify the entered data validity and plausibility.

Queries can result from various sources:

- Manual Checks by data management
- Manual Checks by pharmacovigilance
- Source data verification during on-site monitoring

9.6.2 Source Documents

The source documents are contained in the patient's medical record. Data collected on the eCRFs must be traceable to these source documents in the patient's medical records as far as this is routine documentation. All original source documentation is expected to be stored at the site for the longest possible time required by local applicable regulations. The site will be instructed to notify the Sponsor before any destruction of medical records of study participants.

9.6.3 File Retention and Archiving

The study database and all study-specific documents received by [REDACTED] will be transferred to BI regularly during and after the study period. Archiving will be performed by BI Pharma in accordance with BI SOPs.

To enable evaluations and/or audits from regulatory authorities or the Sponsor, the investigator agrees to keep records, including the identity of participating patients, copies of all CRFs, SAE forms, source documents and adequate documentation of relevant correspondence (e.g., letters, meeting minutes, telephone calls reports). The records should be retained by the investigator according to local regulations, or as specified in the study contract, whichever is longer.

Each site will receive a study site file at study initiation that contains all documents necessary for the conduct of the study and is updated throughout the study. This file must be available for review in the event the site is selected for monitoring, audits, or inspections and must be safely archived for at least thirty years after the completing participation in the study. In the event that archiving of the file is no longer possible at the site, the site will be instructed to notify the Sponsor.

9.7 DATA ANALYSIS

Details on the statistical analyses will be given in a statistical analysis plan (SAP). In brief, the planned analyses will be conducted as follows:

All patients who have received at least one dose of Spiolto® Respimat® or triple combination (free or fixed LAMA + LABA+ ICS) will be included in the analysis; this is the treated set. All analyses will be performed on the treated set (as-treated analysis).

The analyses will relate to the following data:

- primary outcome: Therapeutic success based on mMRC score difference;
- primary outcome: Therapeutic success based on CAT™ score difference;
- secondary outcome: Changes from Visit1 to Visit 2 in the mMRC and CAT™ scores;
- Specialization of attending physician (GP, pulmonologist, internal specialist)

- Patient demographics (gender, age, height, weight)
- Comorbidities (main diagnosis and concurrent diagnosis according to MedDRA, version valid as at the time of database closure)
- COPD related and other concomitant medication (according to the WHO classification, version valid at the time of database closure)
- History of smoking / current smoking and pack years
- Reported number and severity of exacerbations in the last 12 months
- Dyspnea based on mMRC score at visit 1 and visit 2
- Symptom burden based on CAT™ score at visit 1 and visit 2
- Patient satisfaction with inhaler and therapy at visit 2 only; secondary outcome
- General condition of the patient: evaluated by the physician (Physician's Global Evaluation (PGE)), secondary outcome
- Patient's willingness to continue, reason for unwillingness; secondary outcome
- Adverse Drug Reactions (ADR and SADR), fatal AEs, pregnancies
- GOLD spirometric classifications (1, 2, 3, 4) and GOLD patient groups (A, B, C, D)
- Details of current treatment with inhaled respiratory agents at Visit 1
- Details of treatment with respiratory agents during the study
- Reasons for ending treatment during the observation period
- Details of treatment continuation / discontinuation

Descriptive statistics for comparison of baseline characteristics and crude outcome analyses comprise N / mean / SD / min / median / max for continuous variables, while for categorical variables tabulations of relative and absolute frequencies will be presented. Incidence rates and 95% CI will be given where appropriate.

All analyses will be carried out using SAS® statistical software, version 9.4 or higher (██████████).

9.7.1 Main analysis

For the two primary outcomes, as specified in section 9.3.2.1, the comparative treatment effect will be estimated along with 95% confidence intervals.

The estimation of the treatment effect is subject to potential confounding. Therefore, adjusted analyses are required. Multiple analytical approaches will be applied to allow an assessment of the sensitivity of the results to these approaches:

- Propensity score matching (primary analysis; requires data to be discarded from the analysis)

[figure not shown]
Proprietary confidential information © 2019 Boehringer Ingelheim International GmbH or one or more of its affiliated companies

- Propensity score weighting (uses the complete data set)
- Multivariable regression modeling (uses the complete data set)

Multiple imputation will be applied to estimate the propensity score model and the multivariable regression models.

Covariates for adjustment include patient demographics (age, sex), disease characteristics (baseline CATTM / mMRC, exacerbation history, pack-years of smoking, FEV₁, eosinophil levels) and health care provider (GP / pulmonologist). Baseline comparability before and after matching will be assessed using standardized differences.

The comparative effectiveness on the primary endpoints will be determined based on model coefficients (along with 95% confidence intervals) and statistical testing of these coefficients. Since the study is exploratory in nature, no multiplicity adjustment is planned.

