| | | | 
The recent GOLD update supports the design of this study. GOLD 2019 suggests that patients who do not suffer from frequent exacerbations and who present with persistent breathlessness or exercise limitation on LABA/ICS treatment, should either be escalated to triple therapy or switched to LAMA/LABA. A switch from LABA/ICS to LAMA/LABA is suggested in case the initial indication of ICS was inappropriate or if there has been a lack of response to ICS treatment, or if ICS side effects warrant discontinuation.
 
Currently, no prospective clinical evidence is available that supports a direct switch from LABA/ICS to LAMA/LABA instead of moving to triple therapy if an initial indication for ICS use is lacking. Therefore, this study aims to investigate if patients who are symptomatic under LABA/ICS treatment and are switched to LAMA/LABA do not suffer more from dyspnea and symptoms compared to triple therapy.
 |
| Research question and objectives: | 
The primary objective of this NIS is to investigate the changes in dyspnea (as measured via mMRC (Modified Medical Research Council) questionnaire) and symptom burden (as measured via CAT™ (COPD Assessment Test)) in COPD patients who are dyspneic despite LABA/ICS maintenance treatment when switched to either Spiolto® Respimat® in the new reusable inhaler or to any triple therapy (free or fixed-dosed).
 
More precisely, this study aims to assess analyze the comparative effectiveness of Spiolto® Respimat® in the new reusable inhaler vs any triple therapy in changes in dyspnea and symptom burden from each individual patient's difference between baseline and after approximately 12 weeks of treatment.
 
Two primary endpoints will be assessed:
 
• Difference in mMRC (modified Medical Research Council) score at baseline and after end of observation (approx. 12 weeks of treatment, Visit 2)• Difference in CAT™ (COPD assessment test) score at baseline and after end of observation (approx.. 12 weeks of treatment, Visit 2) | | |

| | | | |
|---|--|---------------------------------|--|
| Name of company: Boehringer Ingelheim Pharma GmbH & Co. KG | | | |
| Name of finished medicinal product: Spiolto® Respimat® | | | |
| Name of active ingredient: R03AL06 Tiotropium bromide and Olodaterol | | | |
| Protocol date: 27 May 2019 | Study number: 1237-0087 | Version/Revision: 2.0 | Version/Revision date: 7 June 2019 |

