7.1.6 Intention of the study

This non-interventional study (NIS) aims to investigate alleviation of dyspnea and symptom burden in COPD patients who are symptomatic (dyspneic) despite LABA/ICS maintenance therapy and who are switched to Spiolto® Respimat® in the new reusable inhaler or to triple therapy at the discretion of their attending physician. If a patient has symptoms other than dyspnea that led to a change from LABA/ICS, these patients will also be included into the study - except for those classified as acute exacerbations by the treating physician. Dyspnea will be assessed with the mMRC questionnaire; symptom burden will be evaluated with the CAT™ questionnaire.

The recent GOLD update supports the design of this study by suggesting that patients with persistent breathlessness or exercise limitation on LABA/ICS treatment and not suffering frequently from exacerbations receive

- either addition of a LAMA to escalate to triple therapy or
- a switch from LABA/ICS to LAMA/LABA
 - if the original indication of ICS was
 - inappropriate, or
 - if there has been a lack of response to ICS treatment, or
 - if ICS side effects warrant discontinuation.

The current study aims at strengthening the database on this key therapeutic decision in everyday practice. Currently, no prospective clinical evidence is available supporting a direct switch from LABA/ICS to LAMA/LABA instead of moving to triple therapy if there is no indication for an ICS. Therefore this proposal aims at investigating if patients that are symptomatic under LABA/ICS treatment can be switched to LAMA/LABA and do not do worse compared to a triple therapy.

7.2

DRUG PROFILE

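### The non-inferiority margins that size the study in Protocol 9.5.1 are missing from the analysis text of Protocol 9.7.1 and SAP 7.3, and the primary-outcome labels disagree

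*Protocol*

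**What the plan says.** **Aim.** The Protocol abstract wants to know whether patients "switched to LAMA/LABA do not suffer more from dyspnea and symptoms compared to triple therapy". Section 7.1.6 asks whether they "can be switched to LAMA/LABA and do not do worse compared to a triple therapy".

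**Sizing.** Protocol 9.5.1 computes the numbers "using two-sample t-tests (one-sided alpha-level 2.5% and 90% power"), and "The respective MCIDs are treated as non-inferiority margins": 1 point for mMRC, 2 points for CAT. It then says that "the required sample size for the NIS equals the higher of the two respective estimates", which is the CAT figure of 864. The section calls the calculation a rough guide and says that the authors know of no established margin for either scale.

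**Analysis.** Under Protocol 9.7.1 the "comparative effectiveness on the primary endpoints will be determined based on model coefficients (along with 95% confidence intervals) and statistical testing of these coefficients". No null value, direction or margin is named. SAP 7.3 plans a linear model for the change score, with GEE for matched patients and the baseline value as covariate, and reports estimates with 95% intervals. It mentions a p-value only as an option, for the treatment-by-GOLD interaction.

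**Labels.** Protocol 9.3.2.1 and SAP 5.1 make the two score changes primary, and 9.7.1 follows: "For the two primary outcomes, as specified in section 9.3.2.1". The list in Protocol 9.7 instead calls a therapeutic success based on each score difference primary, without defining it, and puts the score changes among the secondary outcomes. SAP 7.3 counts three primary outcomes. Its history table shows that this number was set deliberately, and SAP 5.1 has three bullets, the third being a CAT categorisation introduced for descriptive use.

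**The concern.** A not-worse question is answered by comparing a confidence limit with a margin. A test of a coefficient, read in the usual way against zero, answers a different question, and the two can disagree on the same data. The plan states the margins where it justifies the sample size and omits them where it says how effectiveness will be judged. As written, the choice between the readings could be made after the results are known, and it can favour either conclusion. The 90% power in 9.5.1 would also be quoted for an analysis to which it does not apply. The conflicting labels add a smaller doubt about which outcome the margins belong to.

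**Working it through.** **Inputs (Protocol 9.5.1).** Margins: CAT 2, mMRC 1. SDs: CAT 7, mMRC 1. One-sided 2.5%, 90% power, two-sample t-test, 22 per group (mMRC) and 259 per group (CAT), 40% loss. The true difference is not stated; 0 is assumed, and this reproduces the stated numbers.

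**1. The plan's own figures.** Power from the noncentral t with 2n − 2 degrees of freedom and noncentrality margin / (SD × √(2/n)):
- mMRC, n = 22: 0.8997. Loss: 22/0.60 = 36.7, so 37 per group and 74 in total.
- CAT, n = 259: 0.9007. Loss: 259/0.60 = 431.7, so 432 per group and 864 in total.

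Both reproduce. The sizing is sound for a margin comparison. A two-sided test of zero at 5% would reject in only 5% of studies under the same assumption of no true difference.

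**2. CAT at 259 per group, SD 7.**
- SE = 7 × √(2/259) = 0.615.
- 95% half-width = 1.9646 × 0.615 = 1.208.
- The margin is met if the estimated deficit is below 2 − 1.208 = 0.792.
- The coefficient is non-significant against zero if the estimate lies within ±1.208.

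An estimate 0.79 to 1.21 points worse is therefore non-significant yet fails the margin. This happens in about 7% of studies if the true deficit is 0 and about 26% if it is 1 point (normal approximation).

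At a true deficit of 2 points, 2.5% of studies meet the margin whatever the SD. The share that is non-significant against zero depends on the SD (range assumed):

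| SD | Non-significant |
|---|---|
| 5 | 0.5% |
| 6 | 3.4% |
| 7 | 9.9% |
| 8 | 19.0% |

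**3. Where the CAT conflict reverses.** The half-width equals half the margin when 1.9646 × SD × √(2/259) = 1, that is at SD 5.79. Below that, some estimates are significantly worse than zero yet within the margin.

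Protocol 9.5.1 does not say whether SD 7 refers to the score or to the change, and this matters:
- If it is the SD of change, a baseline–change correlation of 0.3 to 0.5 (assumed) gives a baseline-adjusted residual SD of 7 × √(1 − r²) = 6.7 to 6.1, and 7.5% to 3.7% non-significant.
- If it is the SD of the score, a baseline–Visit 2 correlation of 0.6 (assumed) gives 7 × √(1 − 0.36) = 5.6, and 1.8%.

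**4. mMRC at 259 per group, SD 1** (taken as the SD of change).
- SE = √(2/259) = 0.0879; half-width 0.173.
- The margin is met up to an estimated deficit of 1 − 0.173 = 0.827.
- An estimate 0.17 to 0.83 points worse is thus both significantly worse and within the margin.

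At a true deficit of 0.3 points the test against zero finds worse in 92.6% of studies (98.9% at SD 0.8, 81.0% at SD 1.2, both assumed), while over 99.9% meet margin 1.

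**5. Both endpoints.** At no true difference, mMRC power for margin 1 exceeds 99.9% with 259 per group. Requiring both margins therefore leaves joint power at about 0.90.

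All these figures use the unadjusted t-test of 9.5.1. The matched, baseline-adjusted GEE will have somewhat different precision.

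**The case against.** The strongest reply is that neither document states a test against zero. Protocol 9.7.1 names no null, and SAP 7.3 plans no main-effect test at all. The 95% interval is planned and the margins are printed in 9.5.1, so any reader can put them together. This stands in part: the probabilities above for the test against zero are conditional on an inferred reading, and what is missing is a rule of interpretation. But an unwritten rule remains optional.

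Second, the study is exploratory: "The primary outcomes are reported in a descriptive manner, will be compared in an explorative manner". That limits the weight of the point. It does not settle which reading answers the not-worse question, and 9.7.1 still says that effectiveness is determined by the coefficients and their tests.

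Third, using the margins as a reporting rule gives formal status to figures that 9.5.1 itself calls unestablished, and an mMRC estimate up to 0.83 points worse would be within the margin. This is fair. It is a reason to repeat that caveat beside the rule and to report such a result both ways.

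Fourth, the labels are largely settled, because 9.7.1 points to 9.3.2.1 and SAP 5.1 agrees. That also stands; the remaining conflict is editorial.

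**Conclusion.** The gap is real and moderate. The analysis text of Protocol 9.7.1 and SAP 7.3 does not contain the margin comparison that 9.5.1 powers at 90%. On the inferred reading against zero, the two approaches disagree often enough to change a conclusion: about 10% against 2.5% for a 2-point CAT deficit at SD 7, and about 93% against over 99.9% for a 0.3-point mMRC deficit at SD 1. These figures assume 259 per group, an unadjusted t-test and the 9.5.1 SDs taken as SDs of the analysed change.

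Three stronger readings are tempting and not supported:
- A reader might infer that the plan will declare patients not worse from a non-significant test. No passage says so.
- A reader might infer that a test against zero is always the laxer route. For CAT this reverses below SD 5.8, and for mMRC the conflict runs the other way.
- A reader might infer that the sample size or the model is wrong. The numbers reproduce, and the two-sided 95% interval already matches a one-sided 2.5% margin comparison.

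The statement of absence covers Protocol 9.7.1 and SAP 7.3 only. Some section numbers, such as Protocol 9.7.2 and SAP 7.5, do not appear in the available text.

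**What to change.** **1. Add a reading rule to Protocol 9.7.1 and SAP 7.3**, for the primary propensity-score-matched analysis on the matched set:
- Define improvement as baseline minus Visit 2 and the contrast as Spiolto minus triple. This sign is a proposal; the responder definitions give thresholds but no sign convention.
- Report the adjusted difference in improvement for each endpoint with its two-sided 95% interval, and read the lower limit against −2 (CAT) and −1 (mMRC), the 9.5.1 margins.
- An interval that crosses the margin is inconclusive.
- An interval wholly below 0 but above the margin is reported as both a smaller improvement and within the margin.
- A non-significant coefficient is not read as not worse.
- State whether an overall statement needs both endpoints; requiring both keeps joint power at about 90%.
- Keep the exploratory label and repeat that established margins are lacking. State whether the 9.5.1 SDs are of the score or of the change.

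**2. Reconcile the list in Protocol 9.7** with 9.3.2.1, 9.7.1 and SAP 5.1, so that the two score changes are primary. Define therapeutic success, or label it secondary if it means the responder outcomes of 9.3.2.2.

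**3. Correct three to two primary outcomes in SAP 7.3.** SAP 5.1 already presents the CAT categorisation as descriptive.

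**Cost.** A few sentences in each document; sample size, data collection and models are unchanged. The price is that some results will have to be reported as inconclusive, or as worse than the comparator and within the margin at once.
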